9.2. Sample Size Determination

A sample size of 80 evaluable participants per treatment group will provide 90% power to detect a difference of 3.1 points for the change from Baseline to Week 12 on the TETRAS composite outcome score between JZP385 and placebo, with a common SD of 6.0 points. This sample size will also provide 91.7% power to detect a 26% between-treatment (assuming JZP385 at 66% versus placebo at 40%) difference in proportion of participants who improved by at least 1 point on the CGI-S from Baseline to Week 12. Assuming a 20% dropout rate, a total of 400 participants (100 participants per treatment group) will be randomized. The sample size calculation for the TETRAS composite outcome score is based on t-test and the CGI-S sample size calculation is based on chi-square test, both tests are 2-sided at the significance level of 0.05.

For the TETRAS composite outcome score, at least 80% power is still achieved if there is a reduction of 0.4 points from the assumption in the difference in mean change from baseline (assuming a constant common standard deviation) or an increase in common standard deviation by 1 point, (assuming a constant difference in means).

9.3. Analysis Sets

For the purposes of analysis, the following analysis sets are defined:

Participant Analysis Set	Description				
Enrolled	The Enrolled Analysis Set will include all participants who provide informed consent for this study.				
	This analysis set will be used to summarize participant disposition, major protocol deviations, and inclusion/ exclusion from the analysis sets as well as reasons for exclusion from each analysis set. Summaries will be presented overall and by the randomization group.				
Safety	The Safety Analysis Set will include all participants who receive at least 1 dose of study intervention. This analysis set will be used for safety analyses, and participants should be summarized according to actual treatment.				
Modified Intent-to-treat (mITT) analysis set	The mITT Analysis Set will include participants who are randomized to any of the JZP385 treatment groups or placebo, receive at least 1 dose of study intervention, and have baseline and at least 1 non-missing within window post-baseline TETRAS composite outcome score. This population will be analyzed for all efficacy endpoints. If a participant in the mITT population does not have any assessment for a particular secondary efficacy endpoint, that participant will be excluded from the analysis of that endpoint.				
PK Analysis Set	The PK Analysis Set will include all participants who receive at least 1 dose of study intervention and have at least 1 postdose evaluable PK concentration. All PK analyses will be based on the PK population.				

9.4. Statistical Analyses

The statistical analysis plan (SAP) will be finalized prior to data base lock and it will include a detailed description of the statistical analyses described in this section.

9.4.1. General Considerations

In general, results will be summarized by treatment group. Categorical variables will be reported as frequency and percent. Continuous variables will be reported as the number of participants, mean, SD, or SE, median, minimum, and maximum. All summaries, statistical analyses, and individual participant data listings described below will be completed using Version 9.3 or later of the SAS Statistical Analysis System (SAS Institute, Inc. Cary, NC).

9.4.1.1. Multiplicity Adjustments

To evaluate the efficacy of JZP385 at doses of 10, 20, and 30 mg/day compared with placebo, pairwise treatment difference between each of the 3 doses and placebo will be tested at the end of Week 12 for the primary and key secondary endpoints.

The family-wise Type I error rate will be controlled at a 2-sided significance level of 0.05. To address the multiplicity issue due to the multiple efficacy endpoints and doses, a fixed

hierarchical testing sequence will be employed. The testing procedure will stop when a p-value exceeds 2-sided significance level of 0.05 (see below).

Statistical hypotheses to be tested (in sequential order):

- 1. Change in the TETRAS composite outcome score from Baseline to Week 12, 30 mg/day versus placebo.
- 2. Difference in proportion of participants who improved ≥ 1 point on the CGI-S from Baseline to Week 12, 30 mg/day versus placebo.
- 3. Change in the TETRAS composite outcome score from Baseline to Week 12, 20 mg/day versus placebo.
- 4. Difference in proportion of participants who improved ≥ 1 point on the CGI-S from Baseline to Week 12, 20 mg/day versus placebo.
- 5. Change in the TETRAS composite outcome score from Baseline to Week 12, 10 mg/day versus placebo.
- 6. Difference in proportion of participants who improved ≥ 1 point on the CGI-S from Baseline to Week 12, 10 mg/day versus placebo.

9.4.1.2. Intercurrent Event Strategies

Discontinuation of study intervention, as specified in Section 7.1, will be considered as intercurrent events.

For the primary and key secondary estimands, the following 2 types of intercurrent events will be considered:

- Discontinuation of treatment due to an AE, for lack of efficacy, or any other reason. Participants who experience this type of intercurrent event will be treated as if they did not experience an intercurrent event (hypothetical strategy). The hypothetical strategy used is defined as the pharmacologic effect of JZP385 compared to placebo assuming the intercurrent event did not happen with continuation of study intervention for the duration of the study. Analyses will be conducted using data collected at time points obtained at or prior to participants' discontinuation of study intervention and combined with imputed values for post-discontinuation time points for which the underlying assumptions are considered appropriate.
- Any change to concomitant antitremor medication use after the initiation of study intervention, including but not limited to the following: 1) starting a new antitremor medication, 2) stopping a concomitant antitremor medication, and 3) a dose or regimen change to current antitremor medication. This type of intercurrent event will be disregarded, and measurements obtained subsequently will be reported and analyzed (treatment policy). Treatment policy is defined as the effect of randomized treatment over the study period regardless of the occurrence of the intercurrent event. In accordance with treatment policy, data collected after this type of intercurrent event will be reported and included in analyses.

If a participant experiences a combination of both types of ICE (eg, change the use of anti-tremor medication and discontinue the study intervention afterwards), each ICE should be treated

independently. Data collected after the change of antitremor medication but on or before the study intervention discontinuation will be included in analyses per treatment policy, the postdiscontinuation data will be handled by hypothetical strategy.

9.4.1.3. Pooling of Investigational Centers

Data from all investigational centers will be pooled for presentation of the main results (eg, demographics, safety, PK, and efficacy). Data may be pooled by region or country as appropriate for exploratory analyses of the primary and key secondary endpoints.

9.4.1.4. Dropouts and Missing Data

The TETRAS composite outcome score will be derived as the sum of items 1 to 11 of the ADL section of TETRAS plus the sum of items 6 (left and right) and 7 of the PS section of the TETRAS (for a total of 14 items on the composite primary outcome). If \leq 3 items of the TETRAS composite outcome score are missing at a specific time point, the mean of the remaining non-missing TETRAS composite outcome score item scores at that point will be used to impute the missing TETRAS composite outcome score item value. The TETRAS composite outcome score will then be calculated as the sum of the observed and imputed item scores. If \geq 4 items of the composite primary outcome are missing, the TETRAS composite outcome score will not be calculated.

For the analysis of the TETRAS composite outcome score, the primary analysis will rely on MMRM, assuming participants who early discontinue the study intervention (defined as an intercurrent event) or missed the assessments due to other reasons would have efficacy outcomes like other participants in their treatment group, randomization stratum, and initial trajectory who completed the study. Sensitivity analyses will adopt control-based drop-out imputation methods to assess the impact on the treatment effect of JZP385 when underlying missing at random (MAR) assumption on the primary MMRM analysis shifted accordingly. A tipping point analysis will further assess the robustness of the primary analysis method.

For the analysis of CGI-S, the primary analysis will adopt a 2-step multiple imputation method and assume data to be missing at random. A tipping point analysis will be conducted as sensitivity analysis to assess the robustness of the primary analysis method.

The details will be further described in the SAP.

9.4.2. Primary Estimand

The primary estimand is a composite outcome score of the sum of modified items 1 to 11 of the TETRAS-ADL and modified items 6 and 7 of the TETRAS-PS. For the primary estimand, the scoring of each of the items 1 to 11 of the TETRAS-ADL subscale as well as items 6 and 7 of the TETRAS-PS will be modified. For TETRAS-ADL, each item will be modified from 5 response items to 4 response items by collapsing options 0 and 1 together and for TETRAS-PS, each item will be modified from 9 response items (due to 0.5 scoring increments) to 4 response items. Each item has a maximum score of 3. As item 6 of the TETRAS-PS includes assessments for both hands, there are a total of 3 items from the TETRAS-PS and 11 items from the TETRAS-ADL that contribute to a 14-item TETRAS composite outcome score. The total range of the TETRAS composite outcome score that will be used for the primary analysis will therefore be 0 to 42.

The attributes of the primary estimand are listed below:

- Treatment: 10, 20, and 30 mg/day JZP385 and placebo.
- Population: Adults with moderate to severe ET.
- Variable: Change from Baseline to Week 12 on the TETRAS composite outcome score.
- Intercurrent Events:
 - Discontinuation of study intervention due to an AE, for lack of efficacy, or any other reason. Participants who experience this type of intercurrent event will be addressed by hypothetical strategy.
 - Any change to concomitant antitremor medication use after the initiation of study intervention (refer to Section 9.4.1.2). Participants who experience this type of intercurrent event will be addressed by treatment policy.
- Summary: Difference in the mean TETRAS composite outcome score from Baseline to Week 12 between each dose of JZP385 and placebo.

For the main estimator analysis, a MMRM will be used to include the difference in the TETRAS composite outcome score from the Baseline Visit to Weeks 4, 8, and 12. The model will include fixed effects for treatment group, week, treatment group by week interaction, baseline TETRAS composite outcome score stratification (≤ 17 or > 17), baseline concomitant antitremor medication stratification (Yes or No), baseline TETRAS composite outcome score by week interaction, baseline TETRAS composite outcome score as a continuous covariate, and week repeated within each participant as a repeated effect. An unstructured variance-covariance matrix will be used to model the correlation among repeated measurements.

For sensitivity analyses, a control-based Pattern Mixture Model (PMM) will be used to explore the possibility of data being missing not at random (MNAR). A supplementary analysis will be conducted with only those participants who have Week 12 TETRAS composite outcome scores. Additional details on sensitivity and supplementary analyses will be provided in the SAP.

Subgroup analyses by randomization stratum, sex, age, and region will be conducted as applicable. Further details will be provided in the SAP.

9.4.3. Secondary Estimands and Endpoints

9.4.3.1. Key Secondary Estimand

The attributes of the key secondary estimand are listed below:

- Treatment: 10, 20, and 30 mg/day JZP385 and placebo.
- Population: Adults with moderate to severe ET.
- Variable: Proportion of participants who improved (≥ 1 point improvement) from Baseline to Week 12 on the CGI-S.

• Intercurrent Events:

- Discontinuation of study intervention due to an AE, for lack of efficacy, or any other reason. Participants who experience this type of intercurrent event will be addressed by hypothetical strategy.
- Any change to concomitant antitremor medication use after the initiation of study intervention (refer to Section 9.4.1.2). Participants who experience this type of intercurrent event will be addressed by treatment policy.
- Summary: Difference in the proportion of participants who improved (≥ 1 point improvement) from Baseline to Week 12 on the CGI-S between each dose of JZP385 and placebo.

The main estimator will be analyzed using the CMH test adjusting for the stratification factors at randomization (baseline TETRAS composite outcome score [≤ 17 or > 17] and the use of concomitant antitremor medication [Yes or No]). The 2-sided p-values from the CMH test, the adjusted treatment difference in proportion using the weighted average of the treatment differences across the strata with the CMH weights, and the associated 2-sided 95% CIs using a normal approximation to the weighted average will be provided.

For the intercurrent event of discontinuation of study intervention due to an AE, for lack of efficacy, or any other reason, under the hypothetical strategy, the primary analysis will adopt a 2-step multiple imputation approach, with MCMC to impute non-monotone intermittent missing followed by a predictive mean matching method to impute the rest monotone missing outcomes.

Sensitivity analysis will be conducted through the tipping point analysis, with further details provided in the SAP.

Supplementary analyses will be performed using the Non-responder Imputation (NRI) method as well as completers analysis with only participants who have Week 12 CGI-S assessment.

9.4.3.2. Secondary Endpoints

For the analysis of CGI-C and PGI-C at Week 12, the CMH test stratified by the randomization stratum will be used for the comparison between each dose of JZP385 and placebo.

For the analysis of change from Baseline to Week 12 on the TETRAS-ADL, TETRAS-PS, TETRAS-PS upper limb score (item 4), and TETRAS total score, the same MMRM models used for the primary estimand will be used.

For the analysis of change of QUEST score from Baseline to Week 12, an analysis of covariance (ANCOVA) model will be used. The model will include treatment group, randomization stratum, and corresponding baseline value as fixed effects.

For the analysis of change of ETEA score from Baseline to Week 12, an ANCOVA model will be used. The model will include treatment group, randomization stratum, and corresponding baseline value as fixed effects.

9.4.4. Tertiary/Exploratory Endpoints

For the analysis of change from Baseline to Weeks 4 and 8 on the TETRAS composite outcome score, TETRAS-ADL, TETRAS-PS, TETRAS upper limb score (item 4), TETRAS total score, the analyses results will be derived from the MMRM used in the Week 12 analysis on the primary estimand and the secondary endpoints.

For the analysis of change from Baseline to Week 12 on modified items 6 and 7 of the TETRAS-PS (where each item is modified from 9 response items [due to 0.5 scoring increments] to 4 response items), the sum of modified items 1 to 11 of the TETRAS-ADL subscale (where each item is modified from 5 response items to 4 response items), and TETRAS total score, the analyses results will be derived from a similar MMRM used in the Week 12 analysis on the primary estimand endpoint.

For the analyses of proportion of participants who improved ≥ 1 point from Baseline to Weeks 4 and 8 on the CGI-S, the CMH test stratified by the randomization stratum will be used for the comparison between each dose of JZP385 and placebo. For the analyses of PGI-C and CGI-C at Weeks 4 and 8, the CMH test stratified by the randomization stratum will be used for the comparison between each dose of JZP385 and placebo.

For the analysis of change in SF-36v2 score from Baseline to Week 12, a descriptive summary at each scheduled visit along with change from Baseline to Week 12 will be tabulated and listed.

The time course efficacy analysis using the sum of modified items 6 and 7 of the TETRAS-PS will be performed with a mixed model. The model will include treatment group, time points, treatment group by time point interaction and the randomization stratum as fixed effects, and participant as a random effect.

9.4.5. Safety Analysis

All safety analyses will be performed on the Safety Population. Safety analyses will be descriptive; no formal statistical testing will be performed.

Adverse Event Analyses:

Adverse events will be mapped to system organ classes and preferred terms using the Medical Dictionary for Regulatory Activities (MedDRA). The participant incidence of AEs, AEs related to study intervention, SAEs, AEs leading to discontinuation, and fatal AEs will be summarized. This overall summary will also provide AEs by maximum severity.

The participant incidence of AEs, AEs related to study intervention, AEs, and AEs leading to discontinuation will also be presented by SOC and preferred term. Preferred term summaries may also be provided.

The participant incidence of an AE will be summarized; if a participant has multiple events with the same PT occurring in different periods, the event will be reported for each of those periods. Multiple increases in severity will only be counted as one AE.

Vital Signs:

For each vital sign parameter, summary statistics will be provided for observed and change from baseline values by scheduled visit.

Protocol JZP385-201-04 Amendment 04

Physical Examinations

Observed and change from baseline values for weight will be summarized descriptively by scheduled visit.

12-lead ECG

Observed and change from baseline values for ECG intervals will be summarized descriptively. QT abnormalities will be assessed; the number and percent of participants with values or change from baseline values exceeding certain thresholds will be tabulated.

Laboratory Evaluations

Observed and change from baseline laboratory evaluations will be summarized descriptively.

C-SSRS

Columbia Suicide Severity Rating Scale parameters will be summarized by scheduled visit.

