- 6. History or presence of gastrointestinal (including prior bariatric bypass surgery), hepatic (including alanine aminotransferase [ALT] or aspartate aminotransferase [AST] ≥ 2 x upper limit of normal [ULN] or total bilirubin ≥ 1.5 ULN), or severe renal impairment or end-stage renal disease, or any other condition that, in the opinion of the investigator, may interfere with absorption, distribution, metabolism, or excretion of drugs. Participants with hyperbilirubinemia who have a history of Gilbert's syndrome may be eligible for the study; participants whose screening laboratory test results demonstrate predominantly unconjugated hyperbilirubinemia must be evaluated to exclude other diagnoses and, subsequently, must have the diagnosis of Gilbert's syndrome established in order to be eligible.
- 7. Presence of significant cardiovascular disease at Screening including but not limited to the following:
 - a. Myocardial infarction within the past year;
 - b. Unstable angina pectoris;
 - c. Symptomatic congestive heart failure (American College of Cardiology/American Heart Association stage C or D);
 - d. Revascularization procedures within the past year;
 - e. Ventricular cardiac arrhythmias requiring automatic implantable cardioverter defibrillator or medication therapy;
 - f. Uncontrolled hypertension, or systolic blood pressure ≥ 155 mmHg or diastolic blood pressure ≥ 95 mmHg (based on the average of triplicate assessments at Screening Visit 1, Screening Visit 2, or Baseline);
 - g. Clinically significant ECG abnormality per the investigator assessment, or Fridericia's corrected QT interval (QTcF) > 450 msec for men and > 470 msec for women, based on the average of triplicate assessments at Screening or Baseline; or

- h. Any history of cardiovascular disease or any significant cardiovascular condition that in the investigator's opinion may jeopardize participant safety in the study
- 8. History or presence of bipolar and related disorders, schizophrenia, schizophrenia spectrum disorders, or other psychotic disorders according to the Diagnostic and Statistical Manual of Mental Disorders, 5th edition (DSM-5) criteria.

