- 9. Current suicidal risk as determined from history, by presence of active suicidal ideation as indicated by positive response to item 4 or 5 on the C-SSRS (within the past 24 months), or any history of suicide attempt; current or past (within 1 year) major depressive episode according to DSM-5 criteria. Participants with stable treated depression are allowed per the judgment of the investigator or the treating medical practitioner and the antidepressant treatment has to be stable for at least 6 months prior to Screening and remain stable for the duration of the study.
- 10. History (within past 2 years at screening) or presence of a diagnosed substance use disorder (including alcohol, tobacco, and cannabis) according to DSM-5 criteria, known drug dependence, or seeking treatment for alcohol or substance abuse related disorder.

Prior/Concomitant Therapy

For the following exclusion criteria, please refer to the Trial Site Binder for a list of examples of prohibited therapies and medications.

- 11. Prior magnetic resonance (MR)-guided focused ultrasound thalamotomy, surgical intervention (eg, deep brain stimulation, ablative thalamotomy, gamma knife thalamotomy), or inability to refrain from using a device for treatment of tremor for the duration of the treatment period.
- 12. Botulinum toxin injection for the treatment of upper limb tremor in the 6 months before screening or planned use at any time during the study.
- 13. Treatment with any medication that could produce tremor taken within 2 weeks or 5 half-lives (whichever is longer) before the evaluation of tremor at the Screening Visit (Screening Visit 1 or 2, as applicable) or anticipated use at any time during participation in the study. *Note:* Regular use of sleep medications or anxiolytics (eg, benzodiazepines) to improve sleep or anxiety is permitted provided it will continue to be used at stable dosages throughout the study (ie, PRN use is not permitted).
- 14. Use of prescription or nonprescription drugs or other products known to be inducers of CYP3A4 that are known to decrease AUC by > 30% (eg, primidone) and which cannot be discontinued at least 4 weeks before Baseline or planned use at any time during the study. *Note:* If a potential participant is taking primidone at screening, it must be discontinued at least 4 weeks prior to Screening Visit 2.

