10.4.1. Vital Signs Markedly Abnormal Criteria

Markedly abnormal quantitative vital signs measurements will be identified in accordance with the following predefined markedly abnormal criteria as specified in Table 6.

Table 6 Vital Signs Predefined Markedly Abnormal Criteria

Variable (unit)	Low	High	
SBP (mmHg)	\leq 90 mmHg AND change from baseline \leq -20 mmHg	≥ 180 mmHg AND change from baseline ≥ 20 mmHg	
DBP (mmHg)	≤ 50 mmHg AND change from ≤ -15 mmHg	≥ 110 mmHg AND change from baseline ≥ 15 mmHg	
Orthostatic SBP (mmHg)	\geq 20 mmHg drop with posture change from supine to standing		
Orthostatic DBP (mmHg)	≥ 10 mmHg drop with posture change from supine to standing		
Pulse rate (bpm)	≤ 50 bpm AND change from baseline ≤ -15 bpm	≥ 120 bpm AND change from baseline ≥ 15 bpm	
Orthostatic pulse rate≥ 30 bpm increase with posture change from supine to standing (bpm)			
Weight (kg)	percentage change from baseline ≤	percentage change from baseline ≥	
Temperature (°C)	-10.0% ≤ 35.0 °C	10.0 % ≥ 39.0 °C	

Note: bpm: Beats per minute. DBP: Diastolic Blood Pressure. kg: kilogram. mmHg: Millimeter of mercury. SBP: Systolic Blood Pressure

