10.5.1. ECG Abnormal Criteria

Abnormal quantitative ECG measurements will be identified in accordance with the following predefined markedly abnormal criteria:

Observed values for QT interval, QTcB interval and QTcF will be classified as follows at each time point:

- > 450 msec
- > 480 msec
- > 500 msec

Change from baseline for OT interval, OTcB interval and OTcF will be classified as follows:

- >30 msec increase from baseline
- >60 msec increase from baseline

A listing of participants meeting markedly abnormal criteria as well as a listing of participants with abnormal ECG overall assessment will also be provided based on the Safety Analysis Set.

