10.6. Other Safety Endpoints

10.6.1. Columbia-Suicide Severity Rating Scale

The Screening/Baseline version of the C-SSRS will be administered to participants at screening visit.

The Since Last Visit version of the C-SSRS will be administered to participants at every scheduled in-clinic after the screening visit 2 up to the Safety Follow-up visit or early discontinuation visit.

The following summaries will be provided for the C-SSRS data by visit and by treatment group:

- Number and percentage of participants with any suicidal ideation (i.e., having responded yes to any of the 5 types of suicide ideation) as well as broken down by type of suicidal ideation
- Number and percentage of participants with any suicidal behavior (i.e., having responded yes to any of the 4 or 5 types of suicidal behavior, as applicable) as well as broken down by type of suicidal behavior
- Number and percentage of participants with any suicidal behavior or any suicidal ideation;
 a subject having reported both suicidal behavior and suicidal ideation will be counted only once
- Number and percentage of participants with self-injurious behavior without suicidal intent

Missing data will not be imputed. All C-SSRS parameters will be presented in the subject data listing.

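### The >450 ms QTcF count in SAP 10.5.1 takes no account of baseline, although women may enter with QTcF up to 470 ms, so it mixes pre-existing values with on-treatment prolongation

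*Protocol*

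**What the plan says.** Protocol 9.4.5, under 12-lead ECG, states that QT abnormalities will be assessed and that "the number and percent of participants with values or change from baseline values exceeding certain thresholds will be tabulated". It gives no numerical thresholds.

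SAP 10.5.1 supplies them under the label "predefined markedly abnormal criteria". It says: "Observed values for QT interval, QTcB interval and QTcF will be classified as follows at each time point". The observed-value categories are >450, >480 and >500 ms. They are the same for men and women and do not refer to the participant's baseline. Separate categories cover increases from baseline of >30 and >60 ms. Participants who meet the criteria are also listed individually.

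Protocol 5.2, Exclusion 7g, sets the entry limit for QTcF at "> 450 msec for men and > 470 msec for women, based on the average of triplicate assessments at Screening or Baseline". Women at 451-470 ms may therefore be randomised.

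Elsewhere the SAP does relate abnormal values to baseline. In Table 6 (SAP 10.4.1) the high systolic pressure criterion is "≥ 180 mmHg AND change from baseline ≥ 20 mmHg", and the diastolic and pulse criteria are built the same way. SAP 10.3 plans shift tables against baseline for laboratory results. No shift table or new-since-baseline count is planned for ECG.

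**The concern.** A reader of an outlier table wants to know how many participants in each arm moved above a threshold after dosing. The >450 ms QTcF row cannot answer this. A woman who met the entry limit and has not changed is counted, and listed as markedly abnormal, alongside a participant whose QTcF rose across 450 ms on treatment.

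Pre-existing cases add a background count to every arm, placebo included, against which a dose-related rise is harder to see. Sex is not a stratification factor (Protocol 4.1), so a chance difference between arms in the number of women near the limit feeds directly into the row. Safety results are descriptive (Protocol 9.4.5), so these raw counts are what readers will compare across the three doses and placebo.

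**Working it through.** The plan states no expected QT count, so there is no figure to reproduce. The check compares the limits, then asks how often an unchanged participant would be counted.

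**Inputs from the documents**
- Entry limits for QTcF: 450 ms for men, 470 ms for women (Protocol 5.2, Exclusion 7g).
- Observed cuts of 450, 480 and 500 ms; change cuts of 30 and 60 ms (SAP 10.5.1).
- On-treatment ECGs at Weeks 1, 4, 8 and 12 (Protocol 1.3).
- 100 randomised per arm (Protocol 9.2).

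**Assumptions, not in the documents**
- Readings are normal around the participant's usual value b, independent between visits, with visit SD 5 to 15 ms and no drug effect.

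**Step 1: overlap of entry limits and cuts**

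| QTcF cut | Man at his limit (450) | Woman at her limit (470) |
|---|---|---|
| >450 | not above | above, by 470 − 450 = 20 ms |
| >480 | 30 ms below | 10 ms below |
| >500 | 50 ms below | 30 ms below |

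Only the >450 ms cut can be met by an eligible entry value, and only by women (on the triplicate average used for eligibility).

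**Step 2: how often an unchanged woman is counted as >450 ms**

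One visit: p = Φ((b − 450)/SD). All four visits: p⁴. At least one: 1 − (1 − p)⁴.

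| Usual value b | SD | One visit | All four | At least one |
|---|---|---|---|---|
| 451 | 5 | 57.9% | 11.3% | 96.9% |
| 451 | 15 | 52.7% | 7.7% | 95.0% |
| 460 | 5 | 97.7% | 91.2% | about 100% |
| 460 | 15 | 74.8% | 31.2% | 99.6% |
| 470 | 5 | about 100% | about 100% | about 100% |
| 470 | 15 | 90.9% | 68.2% | about 100% |

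Here b is the usual value, not a single reading. A woman whose entry reading overstated her usual value would be counted less often.

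**Step 3: do the change rows repair this?**

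Take two women:
- A enters at 465 ms and stays there: change 0, counted as >450.
- B goes from 448 to 470 ms: change 470 − 448 = +22 ms, counted as >450.

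Neither meets >30 ms, so the planned category counts treat A and B alike. Only B newly crossed 450 ms. A newly-above count gives A = 0 and B = 1. A shift table puts A on the diagonal and B off it.

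**Step 4: size, illustration only**

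Assume 50 women per arm and entry QTcF normal with mean 415-430 ms and SD 15-20 ms, truncated at 470 ms. The share at 451-470 ms is [Φ((470 − m)/s) − Φ((450 − m)/s)] / Φ((470 − m)/s).
- m = 415, s = 15: 1.0%, or 50 × 0.010 = 0.5 women per arm.
- m = 430, s = 20: 13.9%, or 50 × 0.139 = 7.0 women per arm.

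The width of this range shows that the documents do not fix the number.

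**The case against.** The strongest reply is that baseline is not ignored. The Protocol 9.4.5 sentence itself covers changes from baseline, SAP 10.5.1 has the >30 and >60 ms categories, and SAP 10.5 adds observed values and changes by visit and a listing over time. Classification at each time point may also produce a Baseline row, giving an arm-level reference. All this is correct, and it confines the point to the observed-value categories. It does not show which participants newly crossed a cut.

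Second, the analysis is descriptive and randomisation balances pre-existing values on average. This stands, and it rules out a claim of systematic bias.

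Third, Table 6 has no uniform value-and-change rule: its orthostatic and temperature rows require no change from baseline. This also stands. The comparison shows that the SAP has such tools, not that it breaks a rule of its own.

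A reader might infer more than the documents support:
- **That such women are counted at every visit.** For a usual value of 451 ms, the chance at all four visits is only 8-11%.
- **That uncorrected QT spoils the result, or mostly counts slow heart rates.** QT, QTcB and QTcF are classified separately, so the QT row changes no QTcF result. No heart-rate distribution is given. By QT = QTcF × (60/HR)^(1/3), a QTcF of 420 ms gives QT 446 ms at 50 bpm (not counted) and 462 ms at 45 bpm (counted). Stratification by antitremor medication also limits imbalance in beta-blockers taken for tremor.
- **That the lowest cut should follow the sex-specific entry limits.** This is a trade-off. A woman going from 442 to 470 ms (+28) would meet neither >470 nor >30 and would leave every QTcF row; the present >450 cut catches her.
- **That the C-SSRS counts share the gap.** Post-dose visits use the Since Last Visit version, so a positive answer concerns that interval. Exclusion 9 and Protocol 8.3.6 also bar more than ideation items 4 and 5.

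**Conclusion.** The point holds for the >450 ms QTcF category in SAP 10.5.1. That category and the accompanying listing combine women who entered legitimately at 451-470 ms with participants whose QTcF was prolonged on treatment, and no planned table separates them. The >480 and >500 ms QTcF cuts do not overlap the entry limits.

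The consequence is a diluted row that is open to chance imbalance. No test, power or sample size depends on it, and no missed or false signal has been demonstrated. That an unchanged woman is usually counted at least once rests on the assumed visit SD of 5 to 15 ms and on independent visits. The figure of 0.5 to 7 women per arm rests wholly on an assumed QTcF distribution and sex split; the true number cannot be derived from the documents. This is a worthwhile, inexpensive improvement and not a flaw that threatens the trial's conclusions.

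**What to change.** In SAP 10.5.1:
- Keep the existing observed-value and change cuts.
- For QTcF, and likewise QTcB, add a shift table of baseline category (≤450, >450 to 480, >480 to 500, >500 ms) by worst post-baseline category, by arm. Alternatively, count a participant in an observed-value category only if the baseline value was at or below that cut.
- Name QTcF as the main parameter for interpretation; the uncorrected QT row may stay as supporting information.
- State how triplicate ECGs are combined, since both options need one baseline value. Entry uses the triplicate average, the general rule in SAP 7.2.1 takes the last repeat, SAP 7.2.3 takes the earliest of same-day values, and SAP 10.5 is silent.

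The cost is SAP wording and one or two table shells, with no new data. If the newly-above count replaces the present rows, raw counts will be smaller; adding the shift table avoids that.
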